15 CLINICAL TRIAL PROTOCOL AMENDMENTS

All appendices attached hereto and referred to herein are made part of this clinical trial protocol.

The Investigator should not implement any deviation from, or changes to the clinical trial protocol without agreement by the Sponsor and prior review and documented approval/favorable opinion from the IRB/IEC and/or notification/approval of health authorities (competent regulatory authority) of an amendment, as required by local regulation, except where necessary to eliminate an immediate hazard(s) to clinical trial patients, or when the change(s) involves only logistical or administrative aspects of the trial. Any change agreed upon will be recorded in writing, the written amendment will be signed by the Investigator and by the Sponsor and the signed amendment will be filed with this clinical trial protocol.

Any amendment to the clinical trial protocol requires written approval/favorable opinion by the IRB/IEC prior to its implementation, unless there are overriding safety reasons.

In case of substantial amendment to the clinical trial protocol, approval from the health authorities (competent regulatory authority) will be sought before implementation.

In some instances, an amendment may require a change to the informed consent form. The Investigator must receive an IRB/IEC approval/favorable opinion concerning the revised informed consent form prior to implementation of the change and patient signature should be re-collected if necessary.

17 APPENDICES

Appendix A General guidance for the follow-up of laboratory abnormalities by Sanofi

NEUTROPENIA

[figure not shown]

Note:

- The procedures described in the above flowchart are to be discussed with the patient only in case the event occurs. If applicable (according to local regulations), an additional consent (e.g., for HIV testing) will only be obtained in the case the event actually occurs.
- For individuals of African descent, the relevant value of concern is <1000/mm³

Neutropenia is to be recorded as an AE only if at least 1 of the criteria listed in the general guidelines for reporting adverse events in [Section 10.4.3](#) is met.

[figure not shown]
THROMBOCYTOPENIA

Note:

The procedures above flowchart are to be discussed with the patient only in case described in the the event occurs. If applicable (according to local regulations), an additional consent (e.g., for HIV testing) will only be obtained in the case the event actually occurs.

Thrombocytopenia is to be recorded as an AE only if at least 1 of the criteria listed in the general guidelines for reporting adverse events in [Section 10.4.3](#) is met.

In ANY CASE, FOLLOW the instructions listed in the box below:

[figure not shown]
1. **INFORM** the Site Monitor who will forward the information to the Study Manager
2. **INVESTIGATE** specifically for malaise with or without loss of consciousness, dizziness, and/or hypotension and/or episode of arrhythmia in the previous 72 hours; rule out muscular injury
3. **PERFORM** the following tests:
 - LFTs: AST, ALT, alkaline phosphatase, total and conjugated bilirubin and prothrombin time / INR
 - CPK, serum creatinine, complete blood count
 - Anti-HAV IgM, anti-HBc IgM, (HBV-DNA if clinically indicated), anti-HCV and HCV RNA, anti-CMV IgM and anti-HEV IgM antibodies
 - Depending on the clinical context, check for recent infection with EBV, herpes viruses, and toxoplasma
 - Hepatobiliary ultrasonography (or other imaging investigations if needed)
4. **CONSIDER** Auto-antibodies: antinuclear, anti-DNA, anti-smooth muscle, anti-LKM
5. **CONSIDER** consulting with hepatologist
6. **CONSIDER** patient hospitalisation if INR>2 (or PT<50%) and/or central nervous system disturbances suggesting hepatic encephalopathy
7. **MONITOR LFTs after discontinuation of IMP:**
 - As closely as possible (or every 48 hours) until stabilization, then every 2 weeks until return to normal/baseline or clinical resolution.
8. **FREEZE** serum sample (5ml x 2)
9. **In case of SUSPICION of GILBERT Syndrome**, a DNA diagnostic test should be done

*If unable to retest in 72 hours, use original lab results to decide on further reporting/monitoring/discontinuation.

Note:

[figure not shown]
- “Baseline” refers to ALT sampled at baseline visit; or if baseline value unavailable, to the latest ALT sampled before the baseline visit. The algorithm does not apply to the instances of increase in ALT during screening.
- See [Section 10.4](#) for guidance on safety reporting.
- Normalization is defined as ≤ ULN or baseline value, if baseline value is >ULN.

ACUTE RENAL FAILURE

Acute renal failure is to be recorded as an AE only if at least 1 of the criteria listed in the general guidelines for reporting adverse events in [Section 10.4.3](#) is met.

SUSPICION OF RHABDOMYOLYSIS

Suspicion of rhabdomyolysis is to be recorded as an AE only if at least 1 of the criteria in the general guidelines for reporting adverse events in [Section 10.4.3](#) is met.

Appendix B Procedure for collection, handling, storage, and shipment of SAR407899 specimens for pharmacogenetic samples

1. SUMMARY OF HANDLING AND SUPPLIES FOR PHARMACOGENETIC SAMPLES

1.1 Sampling Supply Description

Pharmacogenetic specimens	Collection/Storage Tube: 2 vacutainer BECTON Dickinson 6 mL K2 EDTA with HEMOGARD closure,
---------------------------	--

1.2 Summary of handling procedures for pharmacogenetic samples

Sample type(s)	Pharmacogenetic
Blood sample volume	6 mL
Collection tube	a 6 mL Becton Dickinson K2 EDTA VACUTAINER™ Plus tubes with HEMOGARD™ closure (PN367863/4) sterile tubes
Anticoagulant	K ₂ EDTA
Blood handling procedures	Keep blood on ice and frozen within 30 minutes of sampling time. DO NOT CENTRIFUGE BLOOD
Storage conditions	-70°C or colder

2. COLLECTION/HANDLING/PROCESSING OF SAMPLES

The analytical methods used are extremely sensitive. All sampling procedures must be followed accurately.

2.1 Blood pharmacogenetic samples for DNA storage

- **Collection schedule:** Per protocol.
- **Procedure:**
 - Using a **waterproof pen**, write subject ID on label in space provided,
 - Collect 6 mL of blood, using the 6 mL Vacutainer Becton Dickinson K2 EDTA with HEMOGARD Closure provided, and gently invert tube 10-15 times permitting the specimen to mix with the anticoagulant,
 - **Under no circumstances should the tube be centrifuged,**
 - Ensure the sample tube is clearly and appropriately labeled as described above and in detail in Covance laboratory manual,
 - Immediately freeze and maintain the blood in an upright position at -70°C or colder. Samples must be stored on dry ice if a freezer is not immediately available,
 - Complete the laboratory requisition form (provided by Covance) for each sample.

- **Labeling of specimens:**

- Each sample tube should have attached to it the label provided by Covance,

DNA Subject ID:XXX-001-YYY ACT14656 / SAR407899 (preprinted) Bar code (preprinted) Accession number (preprinted)

- In the event of damage or loss of the provided labels, a new label should be immediately requested from Covance.

- **Storage**

- Samples must be kept at -70 °C or colder, organized in a rack in numeric order according to the subject ID, until ready for packaging and shipping.

3. PACKAGING AND SHIPMENT OF DNA PHARMACOGENETIC ANALYSIS

3.2 DNA for pharmacogenetic analysis sample

3.2.1 Packaging and shipment

- Samples and accompanying documents should be packaged according to the detailed instructions in Covance laboratory manual provided at the initiation of the study.
- Samples must be packaged according to IATA Dangerous Goods Regulations, Packing Instructions 650, using the packing materials provided by Covance.
- In the event that the packaging materials or instructions are lost, please contact the study Sponsor.
- Ship samples on dry ice to Covance as described in the Global Study Schedule, using the shipping materials provided.

Note: Additional detailed information can be found in Covance laboratory manual, provided at the beginning of the study. This includes additional details regarding:

- Sample collection kits.
- Sample collection procedures.
- Documentation procedures.
- Packing and shipping instructions.
- Sample kit resupply.
- How to get help.

## LIST OF ABBREVIATIONS AND DEFINITION OF TERMS

AESI:	Adverse Event of Special Interest
CFR:	Coronary Flow Reserve
DBP:	Diastolic Blood Pressure
HR:	Heart Rate
PCSA:	Potentially Clinically Significant Abnormality
PD:	Pharmacodynamic
PK:	Pharmacokinetics
PL:	Physical Limitation
SAE:	Serious Adverse Event
SAQ:	Seattle Angina Questionnaire
SBP:	Systolic Blood Pressure
TEAE:	Treatment Emergent Adverse Event

# **1 STATISTICAL AND ANALYTICAL PROCEDURES**

## **1.1 INTRODUCTION**

The purpose of this document is to provide additional technical details.

A comprehensive and detailed description of strategy and statistical technique used to perform the analysis of data was provided in Section 11 of the protocol (amended clinical trial protocol no 03 dated 18-Apr-2018).

Adverse events will be coded according to the Medical Dictionary for Regulatory Activities (MedDRA version 21.0).

Previous and concomitant medication records will be coded according to the World Health Organization Drug Dictionary (WHO-DD version 2018 MARCH 1).

## **1.2 MODIFICATIONS FROM THE STATISTICAL SECTION OF THE PROTOCOL**

At the time of the early study termination decided by the sponsor, only 10 patients were randomized in the study, and only 8 patients have a post baseline CFR assessed (primary efficacy endpoint) . The number of patients initially planned to be randomized in the study was 78, therefore with such few patients finally enrolled in the study, no formal statistical analysis will be performed. The analysis will be only descriptive, with few summary tables and some additional listings.

The following table gives the changes to the protocol statistical section.

**Table 1 – Statistical analysis changes**

Protocol version	Section number	Description of statistical changes
Amended no 03	11.4.1.2 Compliance	No summary table on compliance will be done. Instead listing with individual treatment intake, and compliance by visits interval will be provided.
	11.4.2.1 Analysis of primary efficacy endpoint	No model will be built. Only descriptive table and listing with information on the uncorrected global CRF will be provided
	11.4.2.2 Analysis of secondary efficacy endpoint	No model will be built for the SAQ-PL. Only descriptive table and listing will be provided
	11.4.2.3 Multiplicity considerations	Not applicable. All results presented are considered informative only.
	11.4.3.1 Adverse events	Incidence tables will be provided as planned. Only one listing will be provided for the treatment emergent adverse events with flag to identify SAE, TEAE leading to treatment discontinuation, AESI.
	11.4.3.2 Laboratory data	No summary statistics will be provided since only local laboratory data are retrieved in this study. Only the incidence of PCSA will be provided, as well as standard listings of patients with PCSAs
	11.4.3.4 Vital signs data	No summary statistics will be provided. Only the incidence of PCSA will be provided, as well as standard listings. In addition Individual graphs for SBP and HR could be provided if necessary
	11.4.3.5 Electrocardiogram data	No summary statistics will be provided. Only the incidence of PCSA will be provided, as well as standard listings
	11.4.4 Analysis of pharmacokinetic and pharmacodynamic variables	No PK nor PK/PD analysis will be performed

### 1.3 DATA HANDLING CONVENTIONS

This section describes the rules and conventions used in the presentation and analysis of data.

In the statistical appendices the following treatment label will be used:

**SAR407899 or Placebo.**

For parameters with possible several evaluations before administration, only the last observation will be used as baseline in descriptive statistics and derivations.

For clinical laboratory parameters with nonnumeric values, the imputed values used for the flags of PCSA will be determined by considering the following rules:

- If database value is '< X', the value used will be X/2
- If database value is '> X', the value used will be X

Descriptive statistics for quantitative parameters will be provided using number of observations (N), mean, standard deviation (SD), standard error of the mean (SEM), minimum, maximum and median.

Descriptive statistics for qualitative parameters will be provided using frequencies (N) and percent (%).

For vital signs parameters, the mean value of the three measures by time-points for the sitting SBP, DBP and HR will be used to determine the PCSA.

***Windows for time points for vital signs***

Vital signs analyzed by time point will be summarized using the time windows given below. If multiple valid values of a variable exist within a time window, the nearest from the targeted time point will be used. In case the time of the drug intake the day of the vital sign assessment is not reported in eCRF (possible when the vital sign assessment did not occur the first day or the last day of the kit number assigned), then the theoretical time will be used.

**Table 2 – Time windows definition for vital signs**

Time point	Targeted time	Time windows
T0H	Just before drug intake	6H00 to 0H00 before drug intake
T1H	1 hour after drug intake	0H30 to 2H00 after drug intake
T3H	3 hours after drug intake	2H01 to 6H00 after drug intake

***Handling missing data for adverse events***

In case of missing or inconsistent information, an adverse event will be counted as a treatment-emergent adverse event, unless it can clearly be ruled out that it is not a treatment-emergent adverse event (eg, by partial dates or other information).

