9.2 SAFETY ENDPOINTS

9.2.1 Adverse events

Refer to [Section 10.4](#) to [Section 10.7](#) for details.

Adverse events, serious adverse events, and adverse events of special interest: spontaneously reported to the Investigator (see [Section 10.4](#)) will be collected from signed informed consent until the End of Study at Day 36.

To ensure the continuing safety of patients in this study, an independent DMC will be responsible for reviewing the safety data on a periodic basis throughout the course of the study as outlined in [Section 6.4.1](#).

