11.4.3 Analyses of safety data

The summary of safety results will be presented by treatment group on the basis of the safety population.

All safety analyses will be performed on the safety population using the following common rules:

- The baseline value is defined generally as the last available value before randomization.
- The analysis of the safety variables will be essentially descriptive and no hypothesis testing is planned.

The following definitions will be applied to laboratory parameters, vital signs and ECG.

- The potentially clinically significant abnormality (PCSA) values are defined as abnormal values considered medically important by the Sponsor according to predefined criteria/thresholds based on literature review and defined by the Sponsor for clinical laboratory tests, vital signs, and ECG.

PCSA criteria will determine which patients had at least 1 PCSA during the TEAE period, taking into account all evaluations performed during the TEAE period, including unscheduled or repeated evaluations. The number of all such patients will be the numerator for the PCSA percentage.

Observation period

- The TEAE observation period is defined as the time from the first dose of IMP up to 7 days after the last dose of IMP.
- The on-study period is defined as the time from randomization until the end of the study (see definition in [Section 6.2.1](#)).

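### The SAP's rule for adverse events with missing or inconsistent information has a double negative that reverses its exception: a minor wording error, but in an operative rule

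*SAP*

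**What the plan says.** SAP 1.3, under its heading on missing data for adverse events, gives a default and an exception in one sentence. An adverse event with missing or inconsistent information is "counted as a treatment-emergent adverse event, unless it can clearly be ruled out that it is not a treatment-emergent adverse event". The evidence that can trigger the exception is described as "eg, by partial dates or other information".

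The status being assigned is defined in Protocol 11.4.3: "The TEAE observation period is defined as the time from the first dose of IMP up to 7 days after the last dose of IMP". Events are recorded before that period opens. Under Protocol 9.2.1 they "will be collected from signed informed consent until the End of Study at Day 36".

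The reduced analysis keeps the outputs that use this status. For Protocol 11.4.3.1, SAP Table 1 states "Incidence tables will be provided as planned" and provides a single listing, restricted to treatment-emergent events, with flags for serious events, events leading to discontinuation and events of special interest. On scale, SAP 1.2 reports that "only 10 patients were randomized in the study".

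Neither document states the missing-information rule anywhere else.

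**The concern.** The exception contains two negatives, *ruled out* and *is not*, which cancel. As written, the records exempted from the default are those that the evidence shows to be treatment-emergent. A conservative rule needs the opposite: exempt only the records shown not to be.

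Classification around the first dose is a real task in this trial. Protocol 6.2.1 allows screening of up to 4 weeks, or up to 6 weeks when CCTA is needed. The baseline stress PET precedes the first dose and, under the flow-chart notes in Protocol 1.3, may be done up to 14 days or up to 4 weeks before Day 1. Some events before dosing can be expected.

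If the sentence were programmed as written, an affected pre-dose event would enter the treatment-emergent tables and an affected on-treatment event would leave them. The second error would be hard to see. Protocol 11.4.3.1 planned a listing of all serious events with on-treatment flags, but SAP Table 1 provides one listing, of treatment-emergent events only. An event wrongly excluded would be absent from the tables and from that listing.

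**Working it through.** The plan gives no figure to reproduce here. The check is logical, followed by simple arithmetic on scale.

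**Step 1: the two readings as rules.** For a record with missing or inconsistent information, the evidence either proves that the event is treatment-emergent (TE), proves that it is not, or leaves the question open.

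- Literal SAP 1.3: counted = NOT (*not TE* is ruled out) = NOT (proven TE).
- Evident intent: counted = NOT (*TE* is ruled out) = NOT (proven not TE).

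| Evidence | Literal rule | Intended rule |
|---|---|---|
| Proven TE | not counted | counted |
| Undetermined | counted | counted |
| Proven not TE | counted | not counted |

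The readings disagree in both states where the evidence settles the matter, and agree where it does not.

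**Step 2: against the period in Protocol 11.4.3.** Take illustrative dates: first dose 25 May and last dose 22 June. Adding 7 days to the last dose, the period runs from 25 May to 29 June.

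- Onset in June, day missing, event ongoing on 10 June. Onset lies between 1 and 10 June, inside the period, so the event is certainly TE. The literal rule does not count it.
- Onset in April, day missing. This is certainly before the first dose. The literal rule counts it.
- Onset in May, day missing. Onset may be 1 to 24 May (before dosing) or 25 to 31 May (inside the period), so status is undetermined. Both rules count it.

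**Step 3: scale.** The input is 10 randomised patients (SAP 1.2). The split by arm is not given, so it is assumed, as is that all 10 were treated and fall in the safety population. The change in an arm's incidence from one misfiled event is 1 divided by the number of patients in that arm:

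- 5 and 5: 1/5 = 20 percentage points in either arm.
- 4 and 6: 1/4 = 25 points, or 1/6 = about 17 points.

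Protocol 11.4.3.1 counts patients with at least one event. The change therefore appears only if the patient has no other event in the category concerned: no other treatment-emergent event for the overall row, or no other event under that term for a term-level row.

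**Step 4: what cannot be computed.** The documents do not say how many adverse events had missing or inconsistent information, so the number affected cannot be estimated.

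**The case against.** The strongest reply is that this is an editorial slip with only one workable meaning. A rule whose default is to count an event as treatment-emergent must have an exception for events that are not; excluding an event because it is proven treatment-emergent contradicts itself. SAP 1.1 also says that the document only adds technical detail to Protocol Section 11, and SAP Table 1 lists no change to the treatment-emergent period. On that view, a partial date that settles the question is decided by the protocol definition. Both readings agree where a default is really needed.

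The effect is also likely to be small. Protocol 10.4.3 asks the investigator for the onset date, Protocol 13.3 provides for data queries, and visits are weekly during treatment. Safety analysis is descriptive without hypothesis testing, and SAP 1.2 drops formal analysis altogether. The incidence of potentially clinically significant laboratory, vital-sign and ECG abnormalities also remains, so the adverse event outputs are not the only safety results.

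Most of this stands, and it limits the severity. It does not make the sentence right. Protocol 11.4.3 defines the period but gives no rule for incomplete information, so the SAP sentence is the only instruction for those records. It gives the correct result only if the programmer departs from the text.

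A reader might infer more: that the treatment-emergent tables are wrong, or that all events with informative partial dates were misclassified. The documents do not support that. Total misclassification is a property of the literal rule in the table under step 1, not an error rate in this trial. Nothing shows that the rule was programmed literally, or that any record fell under it.

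**Conclusion.** The point holds as a minor wording correction to an operative rule. Followed exactly, the SAP sentence reverses classification in both cases where the available information is decisive, contrary to its evident intent and to the period in Protocol 11.4.3.

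Its reach is limited to adverse events with missing or inconsistent information; fully and consistently dated events are not touched. The intended meaning is easy to infer and was probably programmed, so the realised effect is unknown and may be nil. The figure of 20 percentage points is a hypothetical scale for one event. It rests on an assumed split of 5 per arm and on the patient having no other event in that category. It matters only because the trial is so small and because so little else in the adverse event output would reveal a misfiled event.

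**What to change.** Replace the sentence in SAP 1.3 with wording to this effect: *An adverse event whose information is missing or inconsistent is counted as treatment-emergent unless what is available (for example, a partial date) clearly shows that it is not.* Then confirm that the program applies this reading.

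The cost is one sentence and one check of the code. No new data are needed. If the intended rule was programmed, nothing is rerun. If the literal rule was programmed, one condition is reversed and the treatment-emergent tables and listing are rerun.

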***Rules to derive SAQ summary scores***

The rules used to derive the secondary endpoint SAQ-PL, and other summary SAQ summary scores are detailed in appendix B.

***Angina episodes and short-acting nitrate intakes frequency***

The weekly rate of angina episode and short-acting nitrate intakes will be derived as follows:

(Nb of angina episodes (respectively nb of short-acting nitrate intakes) reported during the recall period / duration of the recall period) \* 7

For baseline, only the 7 days before randomization will be taken into account as recall period.

